10.8 Conflict of Interest

The Executive Committee in conjunction with NIDDK has established a policy for all members of the investigative team to disclose all potential (real or perceived) conflicts of interest.

10.9 ClinicalTrials.gov Requirements

The proposed study is a clinical trial and will be registered in ClinicalTrials.gov.

10.10 Other regulatory requirements and Requirements for Investigational New Drug (IND)

The FDA has determined that an IND is not required for the D2d study.

Participant medical insurance companies will not be billed for any study visits or study procedures. Payment for research-related injury will be determined by each site. Study records will be maintained for a minimum of 7 years. If D2d related records will be moved to a different location, the site is required to inform the CC of the new location.

11. SAMPLE SIZE CALCULATIONS AND DATA ANALYSIS

11.1 Sample Size Calculation (Power Analysis)

The primary aim of D2d is to assess whether, in participants at risk for diabetes, oral daily vitamin D₃ supplementation will reduce the rate of progression to incident diabetes when compared to placebo.

The D2d study is designed as an event-driven trial to assure that the intended power to detect the hypothesized treatment effect (hazard ratio = 0.75, see below) is achieved irrespective of the event rate in the placebo arm.

The following considerations were used to determine the required number of events:

- 1) The primary study outcome is “time to confirmed diabetes”.
- 2) The primary hypothesis will be tested at a two-sided type 1 error rate (alpha) of 0.05.
- 3) If vitamin D therapy is superior to placebo, the hazard ratio will be 0.75 in the vitamin D arm as compared to the placebo arm.
- 4) The study is designed to have power of 90% to detect a hazard ratio of 0.75.

Based on these assumptions, the required number of events is 508²⁶⁴. To achieve the intended power, D2d will continue until 508 primary events have occurred.

Based on the following assumptions, it is estimated that the required (i.e. randomized) sample size will be 2,382 participants.

- 5) Participants will be recruited over a 2-year period (“accrual period”)
- 6) The expected study duration will be approximately 4 years plus an end-of-study visit over a period not to exceed three months.
- 7) The incidence rate of confirmed diabetes will be 10% per year (hazard rate = 0.1054) in the placebo group.
- 8) The loss-to-follow-up (i.e. going “off study”) rate will be up to 5% per year of follow-up (hazard rate = .0513).
- 9) If vitamin D therapy is superior to placebo, the hazard ratio will be 0.75 in the vitamin D arm as compared to the placebo group.

The table immediately below displays the expected numbers of incident diabetes cases in the placebo group at each semi-annual visit based on transition probabilities derived from the assumed incidence rates of progression and loss-to-follow-up, and the assumption of constant hazard rates for events and loss-to-follow-up. This calculation also assumes that, when study closeout begins, all participants will return for an end-of-study visit, which will include testing for incident diabetes. The table also displays the expected number of events in the vitamin D supplementation arm if treatment reduces the hazard rate by 25%. Given the assumed uniform rate of recruitment over a period of 2 years, the number of events expected to occur within 2 years after the date of last enrollment or at the close-out visit is 586 (293*2) under the null hypothesis and 521 (293 + 228) under the alternative hypothesis. Thus, the study will be very likely to reach the required number of events within four years if vitamin D supplementation is not effective and all other assumptions are satisfied, and will reach that target of events within the same time period with probability greater than 0.50 if treatment reduces diabetes incidence by 25%.

Table 1. Expected number of events at each six-month visit in the placebo and vitamin D arm (under the alternative hypothesis).

	Visit								Total
	M06	M12	M18	M24	M30	M36	M42	End-of-study	
Placebo	60.4	55.9	51.7	47.8	33.1	20.4	9.4	14.3	293
Treatment	45.6	42.7	40.0	37.5	26.3	16.5	7.7	11.6	228

Number of events is approximate. End-of-study visit will coincide with a scheduled visit (semi-annual or annual).

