completed faster and results disseminated to the scientific community and public earlier, although with a shorter follow-up period, more participants need to be recruited, to ensure sufficient statistical power; (3) adequate follow-up is required to allow progression to diabetes to occur; (4) supplementation is expected to achieve steady state level of plasma 25OHD concentration within 4 months in the majority of participants;^{24,229-231} (4) the rate of progression from pre-diabetes to diabetes is expected to be about 10% per year in the control arm, which is a rate high enough to allow for a statistical comparison with the active arm. After considering all these issues, an average follow up period of approximately 3 years is expected, with early enrollees being followed for approximately 4 years and the sample size was calculated accordingly.

Rationale for lack of run-in period. A run-in period before randomization could identify participants whose 25OHD concentration may not respond to vitamin D or develop side effects and also could identify participants that are likely to become low adherers, thereby increasing adherence to study medications and retention. However, a run-in period was not included in the study design because it would add considerable expense without proportional benefit as the proposed intervention and assessment of outcomes are relatively low-burden and vitamin D supplementation raises 25OHD concentration in all participants (although the degree of rise may vary). Furthermore, external validity may be lessened in studies that include a run-in period.²³²

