7.5 Modification of Study Intervention

If a participant is unable to tolerate the study pills due to safety concerns (i.e. symptom, sign or laboratory abnormality) or for any other reason, study pills will be temporarily held or permanently discontinued (depending on the reason). Specifically, study pills will be permanently discontinued for: hypercalcemia, nephrolithiasis, hypercalciuria and kidney dysfunction, per criteria defined in the Data and Safety Monitoring Plan (DSMP). Study pills will also be held or discontinued at participant’s request. Study pills may be temporarily held for an adverse event (that is unrelated to study pills) or for other reasons. Study pills will be held during pregnancy and lactation. Participants who permanently discontinue study pills will remain in the study and return for all remaining scheduled follow-up visits until study end, consistent with the intention-to-treat principle. The importance of remaining in the study, even if they stop taking the pills, will be emphasized to participants during the informed consent process and at every visit.

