7.6 Adherence with Study Procedures and Study Pills

Participants' adherence to study procedures is critical to the successful conduct of D2d, especially because of its impact on power; therefore, the study will aim to maximize adherence, by taking the following steps: (1) Prevent/minimize potential adherence problems before participant enrollment, as follows: the study design has kept the intervention (i.e. single daily dose study pill regimen) and follow-up procedures uncomplicated; the informed consent process will emphasize the importance of adherence; exclusion criteria include those with higher probability of non-adherence. (2) Maintain/enhance adherence during the trial, as follows: participants will be seen three times during the first 6 months (at baseline, 3-month and 6-months) and every 6 months for the remainder of the study; at the midpoint of each 6-month interval, participants will receive a telephone call to encourage adherence, assess for adverse events or changes to medical history and concomitant medication use and be reminded to report the diagnosis of diabetes outside of D2d or planned (or actual) use of any new medications (especially diabetes medications) and be reminded of their upcoming visit (alternatively, participants may also be contacted via email, or text based on their preference); study staff will provide participants with a personalized study calendar with visit dates; at every visit, participants will also receive information and tips to promote retention and adherence to study procedures; each site PI, co-investigators, research coordinator and staff will be available to answer participants' questions and will maintain a flexible schedule to meet the participants' needs; sites will also employ a variety of site-specific methods to promote retention by maximizing rapport with participants and their families (e.g. holiday and/or birthday cards). (3) Monitor adherence during the study based on pill counts (at every 6-month visit). Individual adherence to study medication will be defined as a pill intake over 80% based on pill counts. If a participant does not meet the adherence minimum target of 80% at any visit, s/he will be reminded of the importance of adherence to the study's objectives, the administration instructions will be reinforced and the site research staff will work with the participant to identify causes that contribute to suboptimal adherence and develop approaches to overcome barriers to adherence. Adherence during the study will also be monitored by measurement of the physiological response biomarker to vitamin D supplementation (plasma 25OHD concentration) at yearly intervals. A pre-specified absolute level of increase in 25OHD concentration cannot be used for adherence for each participant given the individual variation in response to supplementation, although it is expected that adherent participants will have a rise in 25OHD concentration from baseline. *The 25OHD concentration will not be available in real-time as measurements will be conducted at the end of the study.* Planned analyses will test for effect modification by adherence based on (1) adherence based on pills counts and (2) achieved plasma 25OHD concentration (see Section 11).

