8.6 Inactive status

Participants, for safety reasons, personal choice or any other reason, may need to go “off study medication.” However, they will continue with outcomes assessment as planned. Participants who are lost to follow-up but have not gone formally “off study” (i.e. have not provided a verbal or written *withdrawal of consent*) will be termed “inactive” to reflect the possibility that they will resume adherence with study medication and will return for outcomes measurements. Both “inactive” and “off study” participants are included in the estimated attrition rate that went into the sample size calculations.

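### Does the 508-event target overstate power because it leaves out the gradual 25OHD rise and participants who stop their pills?

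*Protocol*

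**What the plan says.** Protocol 11.1 takes a two-sided alpha of 0.05, 90% power and a hazard ratio of 0.75 for vitamin D against placebo, and arrives at 508 events: "The study is designed to have power of 90% to detect a hazard ratio of 0.75". Table 1 rests on "the assumption of constant hazard rates for events and loss-to-follow-up" and gives the "expected number of events in the vitamin D supplementation arm if treatment reduces the hazard rate by 25" per cent.

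The only attrition input is loss to follow-up; the "rate will be up to 5% per year of follow-up (hazard rate = .0513" per year as a hazard). Section 8.6 adds that inactive and off-study "participants are included in the estimated attrition rate that went into the sample size calculations".

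Three other sections bear on the effect that will be observed:
- Section 4.3.5: "supplementation is expected to achieve steady state level of plasma 25OHD concentration within 4 months in the majority of participants".
- Section 7.5: "Participants who permanently discontinue study pills will remain in the study and return for all remaining scheduled follow-up visits until study end". Section 11.2 then counts their events in the assigned arm whatever their adherence.
- Section 7.6 calls adherence "critical to the successful conduct of D2d, especially because of its impact on power".

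Section 11.1.2 links a reduction of about 20-25% to a rise in mean 25OHD from about 20 to 40-45 ng/mL. It then adopts 0.75 after weighing all the cited evidence, and describes it as a 25% risk reduction in the intervention arm.

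**The concern.** Vitamin D cannot act through a 25OHD level that has not yet been reached, and it cannot act in someone no longer taking it. Table 1 nevertheless has the full reduction in place by the first 6-month visit, and no assumption covers people who are off pills but still followed. The loss-to-follow-up rate does not cover them, because it describes people who leave observation.

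The event-driven design gives no protection here. It fixes the number of events, not the hazard ratio, so a diluted effect would be tested with the same 508 events. If 25% is the effect under full exposure, the ITT effect is smaller, the chance of missing it exceeds the planned 10%, and a null result could be read as firmer than it is.

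**Working it through.** **1. The plan's own figure.** The Schoenfeld formula with 1:1 allocation is events = 4(z₀.₉₇₅ + z₀.₉₀)² / (ln HR)².

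- 4 × (1.960 + 1.282)² / (ln 0.75)² = 4 × 10.507 / 0.08276 = 507.8, rounded up to 508.
- Power at 508 = Φ(√(508/4) × 0.2877 − 1.960) = Φ(1.282) = 90.0%.

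The stated target is correct for a hazard ratio of 0.75.

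**2. Does Table 1 apply the full effect from day 0?** Inputs from 11.1: 2,382 / 2 = 1,191 per arm, placebo hazard 0.1054, loss hazard 0.0513. Expected events by M06 = 1,191 × λ/(λ + 0.0513) × (1 − exp(−0.5(λ + 0.0513))).

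- Placebo, λ = 0.1054: 60.4, as printed.
- Vitamin D, λ = 0.75 × 0.1054 = 0.07905: 45.6, as printed.
- Vitamin D with log HR moving linearly from 0 to ln 0.75 over 4 months: 50.3.

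So no delay is built in. That part of the concern is right.

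**3. Power at 508 events if 0.75 is instead a full-exposure effect.** Inputs are the 11.1 hazards, 2-year uniform accrual and a stop at 508 events. The ITT log HR is the event-weighted mean of the log hazard ratio between arms; the vitamin D arm mixes people on pills (HR as in the first column) with people off pills (HR 1). Power = Φ(√127 × |mean log HR| − 1.960). Stopping rates are assumptions, because the documents give none; the effect is taken to vanish at once on stopping, with no restart.

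| Rise in effect | Stopping per year (assumed) | ITT HR | Power |
|---|---|---|---|
| none (as planned) | 0 | 0.750 | 90% |
| linear, 2 months | 0 | 0.758 | 88% |
| exponential, 95% reached at 4 months | 0 | 0.761 | 87% |
| linear, 4 months | 0 | 0.767 | 85% |
| no effect for 4 months, then full | 0 | 0.785 | 78% |
| none | 3% / 5% / 10% | 0.760 / 0.766 / 0.781 | 87% / 85% / 80% |
| linear, 4 months | 3% / 5% / 10% | 0.777 / 0.783 / 0.798 | 81% / 79% / 72% |

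As a check on the 4-month linear row: about 15% of the 508 events fall in the first 4 months, and over that period about half the log effect is missing. The mean log HR is therefore about 0.925 × (−0.2877) = −0.266, or HR 0.766.

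**4. Which reading do the documents support?** Section 11.1 defines 0.75 as a contrast between the two arms. Section 11.1.2 calls it the reduction in the intervention arm and ties it to a group mean 25OHD. Section 11.2 makes ITT the primary analysis. An arm-level ratio under ITT is an average over everyone randomized, and for that quantity step 1 is the complete calculation.

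**5. How far does the 4-month rise reach the endpoint?** The Schedule of Procedures and sections 8.2.2-8.2.3 put no scheduled glycemic test before M06; M03 has safety tests only. Section 9.1 dates onset to the first diagnostic value. Apart from symptom-driven or outside diagnoses, the first cases are thus detected about 2 months after steady state is expected. The model in step 3 treats onset as fixed and irreversible during months 0 to 4, which section 11.2 itself regards as somewhat artificial. The loss from the rise is less certain than the table suggests.

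**The case for a change.** The strongest counter-argument is that 0.75 has no visible reserve for dilution. Section 11.1.2 cites a slope of 4% lower risk per 4 ng/mL. A rise of 20 to 25 ng/mL then gives 0.96⁵ = 0.815 to 0.96^6.25 = 0.775, both weaker than 0.75. With the 35-40 ng/mL expected in 4.3.1.2, it gives 0.96^3.75 = 0.858 to 0.815. On that slope 0.75 is optimistic even at full exposure. The sponsor also recognises dilution elsewhere: section 7.6 on adherence, and SAP section 4 on diabetes medication pulling the effect towards null.

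Much of this stands. Section 11.1 would be clearer if it called 0.75 the ITT average, and the two 25OHD ranges do not match. But the slope is only one of the sources the planners weighed. The others include pooled high-versus-low ratios of 0.59 and 0.62 (11.1.2) and a 28% reduction in a pre-diabetes cohort (4.3.5). If the full-exposure reduction were 28%, power at 508 events would be 93% with the linear 4-month rise alone and 88% with 5% per year stopping added. Whether 0.75 is a sound guess is a judgement made openly on mixed evidence; it is not a flaw in the event calculation. The diabetes-medication issue already has a planned sensitivity analysis in the SAP, and the 25OHD mismatch enters no figure in 11.1.

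**Conclusion.** The plan delivers what it states: 508 events give 90.0% power for an arm-level hazard ratio of 0.75. The observation that no lag or pill-stopping term is written is true, but it becomes a shortfall only on a reading the documents do not give. Its size then depends on a chosen rise (85% to 88% for a linear rise over 4 or 2 months, 78% for a complete 4-month delay) and on a stopping rate with no source (79% with the linear 4-month rise and 5% per year).

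None of the possible remedies is worth making. Raising the target to about 583 events (rise alone) or 714 (rise plus 5% stopping) means 75 or 206 more, reached at about 4.3 or 5.3 years instead of 3.8, on assumptions the sponsor has not made. The targets themselves shift with method, to about 597 and 702 if the averaged hazard ratio is held at its 508-event value. Restating power as 85% or 79% would replace the planners' assumption with an equally debatable one. What remains is a label for 0.75, which the ITT context supplies, and a clerical difference in the expected 25OHD range. The primary analysis is the same in every case.

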pre-diabetes by HbA1c 5.6-6.5% and identified 9% more individuals as having diabetes by HbA1c >7%.²⁷⁵ Data from NHANES show that an additional ~6% of participants are identified as having diabetes when HbA1c >6.5% criterion is used in addition to FPG/2hrPG.^{271,273} In a recent systematic review that examined ranges of HbA1c and progression to diabetes, the A1c range of 6.0 to 6.5% was associated with a 25 to 50% incidence of diabetes over 5 years.²⁷⁶ In the CaDDM trial,²⁴ among 202 fully screened participants with available data on FPG/2hPG/HbA1c, the addition of HbA1c≥6.5% increased the prevalence of newly diagnosed diabetes from 2% to 7% (unpublished data provided by [name]). Finally, in the Pima Indian Longitudinal Study (unpublished data provided by [name]), after excluding participants with diabetes at baseline (based on clinical and the 2010 ADA glycemic criteria), there were 392 participants with pre-diabetes (by 2010 ADA criteria) with mean age of 42 years, BMI 39 kg/m² and HbA1c 5.7%. The cumulative incidence of diabetes during a 5-year follow-up period increased from 36% using the old criteria, to 39% using the new expanded criteria, which represents an increase of 12% in the annual incidence rate if HbA1c is added to the FPG/2hPG criteria.

[figure not shown]
In summary, based on available data in the literature and results of unpublished analyses shown above, it is expected that the addition of HbA1c to the FPG/2hPG diagnostic criteria will increase the number of cases of diabetes diagnosed during follow-up compared to the FPG/2HPG criteria alone. Furthermore, the definition of the main inclusion criterion, pre-diabetes, requiring 2 of 3 criteria (identifying participants at relatively high risk) will increase the incidence rate compared to previous studies. However, the planning committee elected to be conservative in its estimate to ensure adequate power for the primary outcome and has assumed an incidence rate of 10% per year (hazard rate = 0.1054) in sample size calculations.

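### The required sample size of 2,382 does not follow from the hazards printed with it (they give 2,280), and Table 1 rests on a different hazard pair from the one that yields 2,382

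*Protocol*

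**What the plan says.** Protocol section 11.1 works in two steps.

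- **Events.** "The primary hypothesis will be tested at a two-sided type 1 error rate (alpha) of 0.05", and "The study is designed to have power of 90% to detect a hazard ratio of 0.75". This gives 508 events, and "To achieve the intended power, D2d will continue until 508 primary events have occurred".
- **Sample size.** "Based on the following assumptions, it is estimated that the required (i.e. randomized) sample size will be 2,382 participants". The assumptions listed are two years of recruitment, a study of about four years with close-out visits over at most three further months, a placebo incidence of 10% per year with hazard 0.1054, and hazard ratio 0.75. The loss-to-follow-up "rate will be up to 5% per year of follow-up (hazard rate = .0513". Uniform recruitment and constant hazards are added in the text above Table 1.

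Section 11.1.1 repeats that the planning committee "assumed an incidence rate of 10% per year (hazard rate = 0.1054) in sample size calculations".

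Table 1 then gives expected events by visit. The accompanying text assumes that "all participants will return for an end-of-study visit, which will include testing for incident diabetes", and the number of events expected "is 586 (293*2) under the null hypothesis and 521 (293 + 228) under the alternative hypothesis". From this the section concludes that 508 events are very likely within four years if treatment has no effect, and have a better than even chance if the hazard ratio is 0.75. A table note calls the counts approximate. The SAP does not restate the calculation.

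**The concern.** A mismatch shows before any recalculation. A sample size described as the number required for 508 events is followed by a table in which that number yields 521 under the same hazard ratio. Either the requirement or the table uses something other than the listed assumptions.

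What is at stake is traceability and the projected duration. In an event-driven trial, the required sample size and the expected event counts are what the sponsor and the DSMB use to judge whether the target will arrive on time. If the two come from different hazards, nobody can tell which projection the observed event count should be compared with.

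**Working it through.** **Inputs** (Protocol 11.1; 1:1 allocation from 7.3.1): two-sided alpha 0.05, power 90%, hazard ratio 0.75, uniform accrual A = 2 years, total duration T = 4 years, placebo hazard 0.1054, treatment hazard 0.75 × 0.1054 = 0.07905, loss hazard 0.0513, 1,191 per arm at N = 2,382.

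**Step 1: events.** Schoenfeld: 4(1.960 + 1.2816)² / (ln 0.75)² = 507.8, so 508. The plan's figure is reproduced.

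**Step 2: sample size.** With event hazard λ, loss hazard η and h = λ + η,

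P(event) = (λ/h) × [1 − (exp(−h(T−A)) − exp(−hT)) / (hA)], and N = 508 / mean P over the two arms.

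| Hazards (placebo, loss) | P placebo | P treatment | Mean P | N |
|---|---|---|---|---|
| 0.10, 0.05 | 0.2400 | 0.1866 | 0.21327 | 2,381.97, so 2,382 |
| 0.1054, 0.0513 (as stated) | 0.2506 | 0.1951 | 0.2228 | 2,279.7, so 2,280 |
| 0.10, 0.0513 | 0.2395 | 0.1862 | 0.2129 | 2,386 |
| 0.1054, 0.05 | 0.2510 | 0.1955 | 0.2232 | 2,276 |

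The plan's 2,382 is reproduced exactly by the first row only. The stated hazards give 102 fewer, which is 102/2,382 = 4.3% below the printed figure. Other routes tried also miss 2,382:

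- a full three-month close-out (T = 4.25) gives 2,139, which widens the gap;
- Freedman's 515 events with the stated hazards gives 2,311;
- scaling by Table 1's own yield, 2,382 × 508/521, gives 2,323;
- the no-loss N inflated by 15% (the Synopsis attrition maximum) gives 2,434.

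**Step 3: which hazards Table 1 uses.** For each six-month interval: 1,191 × (λ/h)(1 − e^(−h/2)) × e^(−hk/2) × the fraction of participants enrolled early enough to reach the visit, where k is the number of completed intervals.

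| | M06 | M12 | M18 | M24 | M30 | M36 | M42 |
|---|---|---|---|---|---|---|---|
| Placebo, printed | 60.4 | 55.9 | 51.7 | 47.8 | 33.1 | 20.4 | 9.4 |
| Placebo, 0.1054/0.0513 | 60.4 | 55.8 | 51.6 | 47.7 | 33.1 | 20.4 | 9.4 |
| Placebo, 0.10/0.05 | 57.4 | 53.2 | 49.4 | 45.8 | 31.9 | 19.7 | 9.1 |
| Treatment, printed | 45.6 | 42.7 | 40.0 | 37.5 | 26.3 | 16.5 | 7.7 |
| Treatment, 0.07905/0.0513 | 45.6 | 42.7 | 40.0 | 37.5 | 26.3 | 16.4 | 7.7 |

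All 14 cells agree within 0.1 with the stated hazards. The table therefore does not use the pair behind 2,382.

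**Step 4: end-of-study column.** If every participant still at risk is tested at exactly four years, the remaining part-interval adds 19.9 placebo and 16.1 treatment events. The table prints 14.3 and 11.6.

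**Step 5: expected events at N = 2,382 and the chance of at least 508 by four years under hazard ratio 0.75** (normal approximation, SD about 20):

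| Basis | Alternative | Null | Chance of ≥ 508 (alternative) |
|---|---|---|---|
| 0.10/0.05, behind N | 508 | 572 | about 0.51 |
| Table 1 as printed | 521 | 586 | about 0.75 |
| 0.1054/0.0513, all tested at four years | 298.4 + 232.4 = 531 | 597 | about 0.87 |

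With the stated hazards and 2,382 participants, 508 events are expected at about 3.85 years.

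**The case against.** The strongest reply is that nothing depends on the difference. The number randomized is larger than the stated hazards need, the trial runs to 508 events whatever the placebo rate, the duration is given only as approximate, and the loss rate is an upper bound. All of that stands, and it limits the point to a reporting correction.

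It also rules out two stronger readings. A reader might infer that the trial is underpowered; it is not, because power is fixed by the 508-event rule. A reader might also infer that the section's statement about timing is false. It is not: the protocol gives no numerical probability, only better than even under the alternative and very likely under the null. Both hold on all three bases, though on the hazards behind 2,382 the former holds only just, at about 0.51.

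A second reply concerns the end-of-study column: the table is labelled approximate and its derivation is not shown. A reader might infer that the group with 24 to 30 months of follow-up was left out, since omitting it gives 14.4 and 11.7, close to the printed 14.3 and 11.6. The match is not exact and the protocol does not show the calculation, so this is a conjecture. Nor are 20 and 16 the uniquely correct cells. They assume testing at exactly four years, whereas sections 8.1 and 8.2.3 make the end-of-study visit the last scheduled semi-annual or annual visit, and 11.1 allows up to three months for close-out. What survives is that the printed cells are lower than the stated assumption of universal testing would give at four years, while the other 14 cells agree within 0.1. The approximate label does not explain that difference.

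**Conclusion.** The point holds as an internal inconsistency with a small, conservative effect. The required sample size is 102 participants above what its printed hazards give (2,280), and it matches exactly the result of using 10% and 5% as hazards. Table 1 rests on the other pair. The section therefore supports three expected event totals under the alternative for the same 2,382 participants: 508, 521 and 531.

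This rests on Schoenfeld's 508 events, exponential event and loss times, uniform two-year accrual and T = 4, all stated in 11.1. That the percentages were entered as hazards is inferred from the exact match. That 2,382 does not follow from the stated hazards needs no such inference. The cause of the low end-of-study cells remains open.

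**What to change.** Use one hazard pair throughout section 11.1, and make 11.1.1 agree. Either:

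- keep 0.1054 and 0.0513, restate the required sample size as 2,280, and say that 2,382 exceeds it, with about 531 (alternative) and 597 (null) events expected if all participants are tested at four years; or
- keep 2,382 as the required number, restate the hazards as 0.10 and 0.05, with 508 and 572 events expected at four years, and rebuild Table 1 on that pair.

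In either case, state the close-out assumption explicitly (when the last test falls relative to four years, and who receives it) and recompute the end-of-study column and the totals from it, rather than substituting particular cells now.

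The cost is a correction to text and one table. Enrolment, the 508-event target, the stopping rule and the analysis do not change.
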